14.2 Progression Free Survival Time

Population: SAF Analysis Set

Progression Free Survival (PFS) time is defined as the time (in months) from first administration of trial treatment until the first date of PD or death due to any cause.

It will be based on "Assessment of disease based on imaging (according to RECIST 1.1)", "Survival follow-up / Progression disease", "Subject Status / Survival Follow-up", "Anti-cancer treatment after discontinuation", "Radiotherapy after discontinuation", "Surgery after discontinuation" and "Death" eCRF pages.

PFS will be censored in the following scenarios:

- Subjects who do not experience an event (PD or death) will be right-censored on the date of the last evaluable (non missing and non "Not Evaluable") tumor assessment.
- If an event (progression or death without previously documented PD) is observed after more than 2 missed study visits (using visit days as planned in the protocol for calculation) from last tumor assessment, the patient will be right-censored at the date of the last evaluable tumor assessment.
- Subjects who start new anti-cancer treatment prior to an event will be censored on the date of the last evaluable tumor assessment before anti-cancer therapy is given.
- Subjects who do not have a baseline tumor assessment or who do not have any post-baseline
 tumor assessments will be censored on the date of first dose unless death occurred on or before
 the time of the second planned tumor assessment in which case the death will be considered an
 event.

PFS = (date of PD or death/censoring - date of the first dose + 1)/30.4375 (months).

The date of PFS event / censoring will be defined in Table 7.

Table 7 Progression-free Survival Event / Censoring

PFS Event Status		Censoring	Date of event / censoring	
Progressed or died	Before any planned tumor assessment or within two subsequent scheduled tumor assessments after last response assessment of CR, PR or SD	Event	Minimum(Date of PD, Date of death)	
	Otherwise	Censored	Date of last tumor assessment with outcome CR, PR or SD or date of first dose, whatever is later	

PFS Event Status	Censoring	Date of event / censoring
Neither progressed nor died	Censored	Date of last tumor assessment with outcome CR, PR or SD or date of first dose, whatever is later

PFS: progression-free survival, CR = Complete Response, PR = Partial Response, SD = Stable Disease, PD = Progressive Disease.

A swimmer plot displaying some key radiological milestones will be produced for each dose level separately. For each subject, the time from treatment start until end of treatment and end of follow-up (last date known to be alive or date of death) will be represented. In addition, the following information will be displayed: time to best overall confirmed response (CR, PR or SD), time to progression, time to the administration of first anticancer therapy and status at the end of the follow-up (alive or dead).

For subjects alive, the last known alive date will be used to determine the end of follow-up and it will be derived using the following dates:

- Last known alive date collected in the "Subject Status / Survival Follow-Up" eCRF page (SSSTDTC variable from SS SDTM domain to be used)
- · All patient assessment dates:
 - Laboratory assessments using information from "Serology", "Hematology", "Biochemistry", "Coagulation", "Urinalysis", "Microscopic analysis" and "Pregnancy test" eCRF pages (LBDTC variable from LB SDTM domain to be used)
 - Vital signs using information from "Vital signs" eCRF page (VSDTC variable from VS SDTM domain to be used)
 - Performance status using "ECOG Performance status" eCRF page (QSDTC variable from QS SDTM domain to be used)
 - ECG, using information from "Electrocardiogram" eCRF page (EGDTC variable from EG SDTM domain to be used)
 - Tumor assessments using "Tumor assessments" eCRF pages (TRDTC variable from TR SDTM domain to be used)
- Start and end dates of anti-cancer therapies administered after study treatment discontinuation using "Anti-cancer treatment after discontinuation", "Radiotherapy after discontinuation" and "Surgery after discontinuation" eCRF pages (CMSTDTC and CMENDTC variable from CM SDTM domain to be used)
- AE start and end dates using "Adverse events" eCRF page (AESTDTC and AEENDTC variables from AE SDTM domain to be used)
- Study treatment administration dates using "M3541 Administration" and "Radiotherapy Administration" eCRF pages (EXSTDTC variable from EX SDTM domain to be used)

A listing will provide the following information on PFS times: dose level, subject ID, date of first and last M3541 administration, date of event/censoring and relative day, event/censoring reason, time to event in months.

An additional listing on survival follow-up will contain all the fields from "Subject Status/Survival Follow-Up" and "Survival Follow-Up/Progression Disease" eCRF pages.

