• Progression-free survival: time from start of treatment to first assessment of PD or death, whichever is earlier. Subjects alive without PD will be censored at their last tumor assessment, documenting the overall objective response is either complete response (CR), partial response (PR), or stable disease (SD). This rule will also apply to subjects dying later than 12 or 26 weeks

Document No. CC Object No. CC

after their last tumor assessment (ie, censoring subjects who died after 2 missed tumor assessments)

- Objective Response: As assessed by the Investigator using RECIST 1.1
- SoLD: As assessed by the Investigator, using RECIST 1.1 on the irradiated target lesions
- Location of first relapse.

**Follow-up:** During survival follow-up (up to 1 year), further anticancer treatment as well as all subsequent progressions will also be recorded.

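### SAP Table 7, read as written, censors at first dose a subject whose first planned tumor scan shows PD; the SAP 14.2 text and protocol 7.3 count an event unless another rule censors

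*SAP*

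**What the plan says.** SAP 14.2 defines PFS as the time "from first administration of trial treatment until the first date of PD or death due to any cause". Protocol 7.3 has the same events: "time from start of treatment to first assessment of PD or death, whichever is earlier".

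Four bullets in SAP 14.2 then list when PFS is censored:

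- There is no event.
- The event "is observed after more than 2 missed study visits (using visit days as planned in the protocol for calculation) from last tumor assessment".
- New therapy came first: "Subjects who start new anti-cancer treatment prior to an event will be censored on the date of the last evaluable tumor assessment" before that therapy.
- There is no baseline scan or no post-baseline scan. These subjects are censored at first dose, with one exception: "unless death occurred on or before the time of the second planned tumor assessment in which case the death will be considered an event".

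After the bullets comes this sentence: "The date of PFS event / censoring will be defined in Table 7". For subjects who progressed or died, Table 7 has two rows. The event row applies "Before any planned tumor assessment or within two subsequent scheduled tumor assessments after last response assessment of CR, PR or SD". All others are censored at "Date of last tumor assessment with outcome CR, PR or SD or date of first dose, whatever is later".

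**The concern.** The event row has one branch for events before any planned scan and one for events that follow a CR, PR or SD. Progression found at the first planned scan lies between them. It is an ordinary outcome in a palliative population, and it needs no missed visit to occur.

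The gap would not announce itself in programming. The censoring row supplies a default date (first dose) for subjects without CR, PR or SD, so code written to the table runs cleanly and returns day-1 censoring. The PFS listing in SAP 14.2 prints the event or censoring date, the reason and the time, and all three would be wrong for these subjects. The same report would show a best overall response of PD beside a PFS censored on day 1. The error falls on the earliest progressors.

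**Working it through.** The plan states no PFS figure to reproduce, so the check applies both rules to the same subject.

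**Inputs.**
- Tumor scans are planned at PTD 42, 90, 126, 180, 270 and 365, with a window of ±7 days at PTD 42 and 90 (protocol Table 1 and section 7.1.4).
- PFS in months = (event or censoring date − first dose date + 1) / 30.4375 (SAP 14.2).
- Assumption: a Monday start without interruption. FD 5 is then day 5, FD 6 is day 8 and FD 10 is day 12. Under Amendment 4, PTD 1 is the day after the last dose, so PTD n is treatment day 12 + n.

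**PD at the first planned scan, PTD 42, with a baseline scan and no new therapy.**
- Table 7, first branch: the PD is at a planned assessment, not before one. Not met.
- Table 7, second branch: there is no earlier CR, PR or SD, because response assessment starts at PTD 42 (SAP 14.1). Not met.
- Table 7 result: censored at first dose, 1 / 30.4375 = 0.03 months.
- Text: no bullet censors this subject. Event on day 12 + 42 = 54, and 54 / 30.4375 = 1.77 months.
- Across the window: day 47 gives 47 / 30.4375 = 1.54 and day 61 gives 61 / 30.4375 = 2.00 months.
- For subjects enrolled before Amendment 4, follow-up days started on the third day after the last dose (SAP 9). PTD 42 is then day 14 + 42 = 56, and 56 / 30.4375 = 1.84 months. The conflict is the same.

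**Other timings of a first scan that shows PD** (same subject):

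| First scan | Table 7 | 14.2 text | Months if event |
|---|---|---|---|
| PTD 20, unscheduled | Event | Event | 1.05 |
| PTD 35 to 41 | Event if the planned assessment means day 42; censored if it means the visit | Event | 1.54 to 1.74 |
| PTD 42 to 49 | Censored at first dose | Event | 1.77 to 2.00 |
| PTD 90, one scan missed | Censored at first dose | Event | 3.35 |
| PTD 126, two scans missed | Censored at first dose | Event | 4.53 |
| PTD 180, three scans missed | Censored | Censored | – |

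If new therapy came before the PD scan, or there is no baseline scan, both rules censor. As a control, SD at PTD 42 followed by PD at PTD 90 or 126 is an event under Table 7, so the table works once a non-PD assessment exists.

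**How many subjects.** The documents give no first-scan PD rate. At an assumed 20% to 50%:
- of the 8 subjects with data at Amendment 4 (protocol 3.1.5): 8 × 0.20 = 1.6 to 8 × 0.50 = 4, about 2 to 4;
- of the maximum of 30 evaluable subjects (protocol 5.1.1): 30 × 0.20 = 6 to 30 × 0.50 = 15.

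**The case against.** The best defence is intent. The bullets list the situations in which PFS is censored, and PD at an on-schedule first scan is not among them. Table 7 is introduced as fixing the date, not the status, and a sensible programmer would treat baseline as stable disease. The intent probably was to count these subjects as events. But Table 7 has its own status column, and nowhere does the SAP say that baseline counts as SD. The defence shows what the table should say, not that it says it.

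The second defence is that little depends on it, and this stands. PFS is a secondary endpoint, which protocol 8.5.3.1 presents in listings. The SAP adds a swimmer plot that shows time to progression, and progression also appears in the best overall response table and the response listings. No Kaplan-Meier estimate or test is planned.

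A reader might also infer more than the documents support:

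- **That Table 7 wrongly censors every subject with PD on the first scan.** It does not. PD on an unscheduled scan before PTD 42 meets the first branch and is an event. Where new therapy, a missing baseline scan or more than two missed visits applies, the text censors too.
- **That a subject who misses PTD 42 and dies before PTD 90 is also censored against the fourth bullet.** This depends on the reading. If the first branch means that no planned assessment has yet been done, that death is an event and agrees with the bullet.
- **That PFS at the first scan would appear as 100%.** No such rate is planned, and deaths or unscheduled PD before PTD 42 would still be events under Table 7.

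**Conclusion.** The contradiction is real for a subject whose first planned scan (PTD 42 or later) shows PD and to whom no other censoring rule in the text applies. At PTD 42, Table 7 gives censoring at 0.03 months where the text and protocol 7.3 give an event at 1.77 months. The months assume uninterrupted treatment from a Monday start. For scans in the early half of the window (PTD 35 to 41), the conflict also requires that the planned assessment means the visit, not the nominal day.

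The counts above rest wholly on an assumed PD rate and indicate scale only. The harm is limited to the listed PFS status, date, reason and time. The DLT analysis, the MTD and dose decisions are unaffected. Because the rule gives a wrong value for a secondary endpoint and contradicts its own section, it should be corrected before the PFS data are programmed.

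**What to change.** Change the Table 7 event row so that the assessment limit runs from the last evaluable assessment without PD or, if there is none, from the first dose. PD at the first planned scan is then an event, dated at the earlier of PD and death.

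In the same edit:

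- **Use one missed-assessment limit in table and text.** The table allows events up to the second scheduled assessment; the text censors only after more than two missed visits. With the new anchor alone, a first scan at PTD 126 showing PD, after two missed scans, would still be censored by the table and an event in the text.
- **Add the bullets' rules on new anti-cancer therapy and missing baseline scans to Table 7.** Without them, the revised row would turn some subjects whom the bullets censor into events. Protocol 8.3.2 lists the onset of other anticancer therapy as a PFS endpoint while the SAP censors for it, so the sponsor should settle that rule before copying it into the table.

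The SAP should not state that table and bullets are the same rule until these points agree. The cost is one revision of Table 7 and its bullets, with no new data, visits or analyses.

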14.3 Sum of Lesion Diameter for Irradiated Lesions

Population: SAF Analysis Set

The sum of lesion diameters (longest for non-nodal lesions, short axis for nodal lesions) for all irradiated lesions will be calculated on the basis of "Tumor assessment (according to RECIST 1.1) - Target lesions" and "Irradiated lesions location" eCRF pages to investigate response of irradiated lesions.

A waterfall plot with all subjects from all cohorts will be provided. Bar height will represent the best percentage change from baseline in sum of diameters, calculated using irradiated lesions only. The confirmed BOR (based on all lesion, i.e. also taking non-irradiated lesions into account) will also be presented as an annotation on each vertical bar. Subjects with no baseline tumor assessment or without any post-baseline tumor assessment will not be included.

In addition, a spider graph to investigate the evolution in time of each target lesion will display the percentage change from baseline in lesion size against the treatment day. One graph per subject will be produced with one curve per lesion, clearly specifying lesion location and distinguishing irradiated from non-irradiated lesions. Subjects with no baseline tumor assessment or without any post-baseline tumor assessment will not be included.

14.4 Location of Disease Progression

Population: SAF Analysis Set

Location of disease progression will be defined as location where tumor size increase has been observed as well as the location of the newly observed lesions.

A listing including all subjects with progressive disease ('Overall Response' = 'Progressive disease' from "Assessment of disease" eCRF page) will be produced. For each subject, all locations for the following lesions will be included:

- Non-target lesions (from "Tumor assessment (according to RECIST 1.1) Non-Target lesions" eCRF page)
- New lesions (from "Tumor assessment (according to RECIST 1.1) New lesions" eCRF page)

Lesions within the irradiated field will be flagged. Specifically:

- Irradiated target and non-target lesions will be derived from "Irradiated lesions location" eCRF page;
- Irradiated new lesions will be derived using the free text lesion description reported in the "Tumor assessment (according to RECIST 1.1) New lesions" eCRF page.

CCI

15 Safety Analyses

The subsections in this section include specifications for summarizing safety endpoints that are common across clinical trials such as adverse events, laboratory tests and vital signs.

The primary endpoint of this trial is to evaluate the occurrence of DLTs. This endpoint is described in section 15.1.

Secondary safety endpoints are:

- Occurrence of treatment emergent adverse events (TEAEs), grade ≥3 AEs, SAEs, and deaths (graded according to the NCI CTCAE v4.03)
- Results of laboratory tests, physical examination (reported as AEs), vital signs, ECGs including QTcF.

All safety analyses will be performed on SAF Analysis Set and according to the as-treated principle.

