# 7.3 Efficacy Assessments

For all subjects, tumor response assessment will be performed by CT scan or MRI (if MRI is used, CT of chest is mandatory) of the chest / abdomen / pelvis (plus other regions as specifically required for specific tumor types) and other established assessments of tumor burden if CT / MRI imaging is insufficient for the individual subject. All the scans performed at Baseline and other imaging performed as clinically required (other supportive imaging) need to be repeated at subsequent visits. In general, lesions detected at Baseline need to be followed using the same imaging methodology and preferably the same imaging equipment at subsequent tumor evaluation visits.

A brain CT / MRI scan (either, with contrast preferred) is required at Screening if not performed within the previous 6 weeks. Thereafter brain CT / MRI scan should be performed, if clinically indicated by development of new specific symptoms. A bone scan should be performed at Screening and beyond as clinically indicated. Skin metastasis can be used as target lesions according to RECIST 1.1 using measurements by caliper, if they fulfill RECIST 1.1 for target lesions as described below. The presence of new cutaneous lesions will be considered diagnostic of progression for RECIST 1.1, even if not imaged. For each subject, the Investigator will ensure appropriate assessment of the irradiated lesion to follow for determining response: CT or MRI images of primary and / or metastatic tumor masses, physical examination findings. All available images collected during the study period will be considered for the follow up of the subject (to determine further additional treatment needs). The measure(s) to be chosen for sequential evaluation during the study have to correspond to the measures used to document the progressive tumor status that qualifies the subject for enrollment. The tumor response assessment will be assessed and listed according to the Schedule of Assessments (see Table 1).

Bone scans are to be performed according to local and institutional standards.

The following endpoints will be derived based on appropriate tumor assessments according to RECIST 1.1 overall and for lesions within an irradiated field, including those after the end of study treatment until first assessment of PD:

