#### 8.3.3 Exploratory Endpoints

The exploratory endpoints are the:

[figure not shown]
- SoLD, as assessed by the Investigator, using RECIST 1.1 on the irradiated target lesions
- Location of disease progression as assessed by the location where tumor size increase has been observed as well as the location of the newly observed lesions
- Absolute values and changes over time of proteins that may be affected by ataxia-telangiectasia mutated (ATM) inhibition in blood (eg, phospho-ATM) during exposure to M3541

• •

• Changes from baseline over time of the total blood cell count and cell subset type of immune cells (eg, T cells, B cells, natural killer cells) during exposure to M3541

• 🖌

Document 1	No. CC
Object No.	CCI

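### The SAP 14.4 listing for location of disease progression omits target lesions and takes in every non-target lesion, so it does not deliver the endpoint as SAP 14.4 itself defines it.

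*SAP*

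**What the plan says.** The protocol's exploratory endpoint (8.3.3) reads "Location of disease progression as assessed by the location where tumor size increase has been observed", to which it adds the sites of newly seen lesions. SAP 14.4 repeats the definition: "Location of disease progression will be defined as location where tumor size increase has been observed", again with new lesions added. Neither text excludes target lesions.

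Protocol 7.3 names a location-of-first-relapse item among the endpoints to be derived "according to RECIST 1.1 overall and for lesions within an irradiated field". The distinction between inside and outside the radiation field is therefore part of the plan.

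SAP Table 1 (section 5) assigns this endpoint to SAP 14.4. The single output there is "A listing including all subjects with progressive disease", taken from the overall response on the disease-assessment page. Its content is fixed by the sentence "For each subject, all locations for the following lesions will be included". Two bullets follow: non-target lesions, from the non-target eCRF page, and new lesions, from the new-lesions eCRF page.

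Lesions in the irradiated field are then to be flagged. For that step the SAP says "Irradiated target and non-target lesions will be derived from" the 'Irradiated lesions location' page. The field status of new lesions is to be taken from their free-text description.

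**The concern.** The definition, the inclusion list and the flag rule in SAP 14.4 do not agree. The definition turns on growth. The lesions whose diameters the SAP follows over time are the target lesions (SAP 14.1 and 14.3), and those are the class left out. The flag rule then gives a source for the irradiated status of target lesions that the list never brought in.

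The list also goes wrong in the other direction. It asks for all locations of non-target lesions with no condition that they progressed. A site that did not progress can therefore appear in an output titled location of progression.

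Protocol 3.1.3 expects M3541 to strengthen the local effect of radiotherapy, so growth of an irradiated target lesion is a direct sign of local failure. SAP 14.3 builds its irradiated-lesion sum from the target-lesion page, which shows that irradiated lesions are expected among the target lesions.

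**Working it through.** No arithmetic applies, and the plan states no figure to reproduce. The check compares what the definition requires with what the listing contains, and then looks for another output that fills the gap.

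**Step 1: lesion classes in SAP 14.4.**

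| Lesion class | Covered by the definition? | In the inclusion list? | Named in the flag rule? |
|---|---|---|---|
| Target | Yes, if it grew | No | Yes |
| Non-target | Yes, if it grew | Yes, all of them, with no growth condition | Yes |
| New | Yes | Yes | Yes |

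The definition and the flag rule each cover three classes. The list covers two, and one of those is too wide.

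**Step 2: what the listing shows if programmed literally.** Every subject with an overall response of PD enters, whatever the cause.

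- PD from target growth only, no non-target lesions: the subject qualifies but has no lesion to show.
- PD from target growth only, stable non-target lesions present: the stable sites appear and the progressing site does not.
- PD from target growth and a new lesion: the new site appears and the target site does not.
- PD from one of several non-target lesions: all non-target sites appear, and 14.4 gives no rule for marking the one that progressed.
- PD from a new lesion only: the new site appears correctly, beside every non-target site.

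The listing fails outright in the first two cases, is incomplete in the third, and fails to separate progressing from other sites in the last two where non-target lesions exist.

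**Step 3: other outputs.**

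- SAP 14.3 plans one graph per subject with a curve for each target lesion, giving percentage change from baseline, lesion location and irradiated status.
- SAP 14.1 plans by-subject listings of lesion site, type, imaging date and size, with the target-lesion page among the sources. It also plans listings of response by lesion class and overall, and of irradiated lesion locations.

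A reader could find the date of PD in the response listing, check the target-lesion response at that date, read the individual diameters, and match them to field status. The information exists in the report. No planned output makes that link or names the site of progression.

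**The case against.** **The listing may be complete in the sponsor's file.** The flag rule makes full sense only if target lesions are listed, so a first bullet could have been lost when the document was converted to text. This cannot be excluded. The list shows no gap or redaction mark, however, and the sponsor can settle it by looking. If the bullet is there, the omission of target lesions falls away. The unrestricted entry of non-target lesions remains.

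**The detail may sit elsewhere.** SAP 18 places table, listing and figure specifications in a separate document, which could add a lesion-status column. That would help to separate progressing from stable non-target sites. It would not by itself bring in a class that 14.4 leaves out of an explicit list.

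**A stronger reading is tempting.** A reader might infer that target-lesion progression, or in-field failure generally, is not shown anywhere, or that in-field progression is systematically under-reported. The documents do not support this. SAP 14.3 displays each target lesion by location and irradiated status, and SAP 14.1 lists the raw sizes. In-field non-target and new lesions are flagged in 14.4 itself. The gap is confined to one listing and, within it, to growth of target lesions. The documents do not say what share of irradiated lesions will be target lesions.

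**The endpoint is exploratory and descriptive.** That stands, and it limits the weight of the point. It does not make the listing agree with its own definition.

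**Conclusion.** Wrong as written, minor. Followed to the letter, the only output specified for this endpoint omits the progressing site for any subject whose PD comes from target-lesion growth alone, and may show sites that did not progress instead. This is a stated rule that gives a wrong result, not merely missing detail.

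The number of subjects affected cannot be derived from the documents. The effect stops at this listing: DLT, best overall response and PFS use other rules and do not change.

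The conclusion assumes that the two-bullet list is complete and that the separate output specifications do not override it. The flag rule suggests that target lesions were meant to be included and were dropped in drafting.

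**What to change.** In SAP 14.4:

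1. Add target lesions to the inclusion list, with the 'Target lesions' eCRF page as source.
2. Identify which target and non-target lesions progressed at the assessment where PD was recorded, by reference to RECIST 1.1, which the SAP already adopts. State the earlier measurement against which an increase in a target lesion is judged, since 14.4 does not give one.
3. Keep the irradiated flag for all three lesion classes, with the sources already named.

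The cost is one more source page and a progression marker in a listing already planned. The target-lesion and irradiated-location pages are used in SAP 14.1 and 14.3, so no new data are needed.

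A table of PD as in-field only, out-of-field only or both, by dose level, would be useful but is optional. The protocol does not ask for it, and it would be an additional derivation.
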